      - 4.4.1.2. Secondary
        - 4.4.1.2.1. Change in volume of contrast enhancement
        - 4.4.1.2.2. Change in volume of necrosis

- 4.4.1.2.3. Change in volume of T2 edema
- 4.4.1.2.4. Steroid usage
- 4.4.2. Results of the Data analyses will be reported over all as well as by stratifying with respect to:
  - 4.4.2.1. Radiation prescription dose
  - 4.4.2.2. Lesion volume
  - 4.4.2.3. Presence of comorbidities: Hypertension, Diabetes
- 4.4.3. As per the design, at the first stage we would evaluate the results by identifying when we have 8 lesions with necrosis. If at that stage, we have 52 or more lesions in the study then that would confirm we should continue to complete the study with all 134 lesions. At that stage, if we find 14 or less lesions with radiation necrosis, we would then claim that the study has met its objective of a 50% reduction in incidence of radiation necrosis (from 15% to 7.5%). (see Appendix A)
- 4.4.4. Summary of Data Submission (See Appendix B)

Follow MRI Form (MF)

- 4.4.4.1. Enrollment Form (EF)
- 4.4.4.2. Initial Evaluation Form (IF)
- 4.4.4.3. Treatment Form (TF)
- 4.4.4.4. Follow Up Form (FF)
- Within 2 wks of registration Within 2 wks of registration At the end of radiosurgery
- Every 3 months for 1 year
- Every 3 months for 1 year
- 4.4.5. Treatment Form (TF) will be completed by treating physician.
- 4.4.6. MRI documentation

4.4.4.5.

- 4.4.6.1. The contrast-enhanced MRI performed pre-radiosurgery and every 3 months post-radiosurgery will be evaluated by the investigators: REW, JB, LI. Form MF will be completed by investigator LI.
- 4.4.6.2. Radiation necrosis will be defined as previously reported by Blonigen et al. (4):

A combination of criteria will be used including appearance on serial MRI scans, MR Spectroscopy and histology (when available). It will be further described as the following: (1) patient with radiographic changes with a requirement of steroid therapy, (2) 2 consecutive scans with persistent MRI changes consistent with radiation necrosis, (3) findings suggestive of radiation necrosis on MR Spectroscopy, or (4) histological evidence of radiation necrosis.

- 4.4.6.3. Once radiation necrosis is identified by the treating physician, parameters will be quantified using standard radiation oncology software tools by an investigator: LI. The volume of contrast enhancement, T2 edema and necrosis will be quantified.
- 4.5. Data storage and confidentiality

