  - 4.5.1. Data will be maintained in a password protected database and will only be accessed by the listed investigators. The information gathered will not be used or disclosed for any other purpose other than this specific research project.

- 5. Estimated period of time to complete the study.
  - 5.1. It is estimated that the patient recruitment period will be 2 years and the follow up period will be one year. Total estimated time to complete the study is 3 years.
- 6. Human Subjects: Describe the characteristics of the research population:
  - 6.1. Subjects will include patients receiving or planning to undergo single fraction or five fraction radiosurgery for a metastatic brain tumor.
  - 6.2. The demographics of the study population are expected to reflect the general population with intracranial metastatic tumors. Only adults  $\geq$  18 years of age will be included in the study.
  - 6.3. Recruitment:
    - 6.3.1. Patients seen at the University of Cincinnati Brain Tumor Center will be directly recruited by the treating physician.
  - 6.4. This study is estimated to require 49 patients. In a recently published study performed at the University of Cincinnati (4), patients recruited to the study had an average of 2.75 metastatic lesions. Each lesion was treated independently when analyzing the incidence of radiation necrosis. Using this same method, a total of 134 lesions are necessary to show a 50% effective reduction in radiation necrosis with our supplement. This would be estimated to require 49 patients.
  - 6.5. Inclusion Criteria:
    - 6.5.1. Patients about to undergo or currently receiving single or five fraction radiosurgery for a metastatic brain tumor.
    - 6.5.2. Diagnosis of a metastatic brain tumor may be accomplished by histologic confirmation or by clinical confirmation by the treating physician based on MR Imaging characteristics in the setting of a known history of cancer.
    - 6.5.3. Availability for follow up
    - 6.5.4. Ability to give informed consent.
    - 6.5.5. Age  $\geq$  18 years
    - 6.5.6. Patients who have had partial or total resection of a metastatic tumor are eligible.
  - 6.6. Exclusion Criteria:
    - 6.6.1. Known sensitivity to vitamin E or Trental
    - 6.6.2. Pregnant or nursing women.
    - 6.6.3. Recent intracranial bleed or retinal hemorrhage

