# **TO DETECT RN REDUCTION FROM 15% (HISTORICAL) to 7.5%** (a 50 % reduction)

#### Possible Designs For P0=0.850, P1=0.925, Alpha=0.050, Beta=0.200

N1	R1	РЕТ	Ν	R	Ave N	Alpha	Beta	Constraints Satisfied
52	44	0.528	134	120	90.69	0.047	0.2000pti	mum & Minimax

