#### **Report Definitions**

N1 is the sample size in the first stage.
R1 is the drug rejection number in the first stage.
PET is the probability of early termination of the study.
N is the combined sample size of both stages.
R is the combined drug rejection number after both stages.
Ave N is the average sample size if this design is repeated many times.
Alpha is the probability of rejecting that P<=P0 when this is true.

Beta is the probability of rejecting that P>=P1 when this is true.
P0 is the response proportion of a poor drug.
P1 is the response proportion of a good drug.

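### The success cut-off is one radiation necrosis count that fits only 134 lesions; the plan does not say whether 134 lesions or 49 patients ends accrual, or what cut-off applies at another total

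*Combined protocol and SAP*

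**What the plan says.** Section 4.4.3 states the final decision as a bare count: "if we find 14 or less lesions with radiation necrosis, we would then claim that the study has met its objective". The only total attached to it comes from the preceding sentence, where passing the first stage means that "we should continue to complete the study with all 134 lesions".

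Appendix A gives one design for a reduction from 15% to 7.5%, under "Possible Designs For P0=0.850, P1=0.925, Alpha=0.050, Beta=0.200". Its row begins "52 44 0.528 134 120 90.69 0.047": 52 lesions in stage 1 with rejection number 44, 134 lesions in all with rejection number 120, and alpha 0.047. The report definitions add that "R is the combined drug rejection number after both stages".

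Section 6.4 moves from lesions to patients. In the institution's earlier study, "patients recruited to the study had an average of 2.75 metastatic lesions". Lesions are to be analysed as independent units, 134 are needed, and "This would be estimated to require 49 patients".

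No section says whether accrual closes at 49 patients or at 134 lesions. None gives a cut-off for any other total or says how surplus lesions in the last patient are counted.

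**The concern.** Patients are enrolled and lesions are counted. Each patient brings a whole number of lesions, so 49 patients yield 134 lesions only on average, even if every lesion is observed. A fixed RN count keeps its stated error rate only at the total for which it was derived. With fewer lesions the same count is easier to meet when the treatment does nothing; with more lesions it is harder to meet when the treatment works.

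In a single-arm trial whose conclusion rests on one count, this bears directly on the claim of success. It also leaves the cut-off for an unplanned total to be chosen after the RN count is known.

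**Working it through.** **Inputs.** From Appendix A: RN 15% under the null and 7.5% under the alternative; stage 1 of 52 lesions, continuing with 45 or more RN-free (7 or fewer RN); total 134; rejection number 120. By Appendix A's own definition, success needs 121 or more RN-free lesions, that is 134 − 121 = 13 or fewer RN. From section 6.4: mean 2.75 lesions per patient, 49 patients, independent lesions. The spread of lesions per patient is not given and is assumed below.

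**Formula.** For total N and cut-off c, with RN probability p,

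P(success) = Σ over x = 0 to 7 of Bin(x; 52, p) × P[Bin(N − 52, p) ≤ c − x].

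Alpha is this at p = 0.15 and power at p = 0.075.

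**Reproducing the plan.** At N = 134 and c = 13: probability of early termination 0.528, average sample size 90.69, alpha 0.047. All three agree with Appendix A. Power is 0.856, so beta is 0.144, better than the printed 0.200. For patients: 134 / 2.75 = 48.7, rounded up to 49, and 49 × 2.75 = 134.75 expected lesions.

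**Holding the count fixed while the total varies.**

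| Lesions | 13 RN: alpha | 13 RN: power | 14 RN: alpha | 14 RN: power |
|---|---|---|---|---|
| 120 | 0.112 | 0.914 | 0.164 | 0.939 |
| 130 | 0.061 | 0.876 | 0.097 | 0.916 |
| 133 | 0.0504 | 0.861 | 0.082 | 0.906 |
| 134 | 0.047 | 0.856 | 0.077 | 0.903 |
| 140 | 0.031 | 0.823 | 0.053 | 0.880 |
| 150 | 0.015 | 0.757 | 0.027 | 0.831 |

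At 13 RN there is no slack below 134: one lesion fewer already exceeds 0.05. Stage 1 as worded in 4.4.3 ("at the first stage we would evaluate the results by identifying when we have 8 lesions with necrosis") barely changes this; 14 RN at 134 lesions gives 0.078 instead of 0.077.

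**If accrual ends at 49 patients.** Three assumed distributions with mean 2.75, from narrow to wide. The SD of the total is 7 × √(variance per patient).

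| Assumed spread | SD of total | 90% range | P(total < 134) | P(total = 134) | Averaged alpha, 13 RN |
|---|---|---|---|---|---|
| 1 + Binomial(4, 0.4375) | 7 × √0.984 = 6.9 | 123-146 | 43% | 6% | 0.049 |
| 1 + Poisson(1.75) | 7 × √1.75 = 9.3 | 120-150 | 45% | 4% | 0.052 |
| Geometric | 7 × √4.8125 = 15.4 | 111-161 | 49% | 3% | 0.064 |

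**If accrual runs to at least 134 lesions.** Under the same three spreads, the mean overshoot is about 1 to 2 lesions, the 95th percentile of the total is 137 to 140, and exactly 134 occurs in about 36% of runs. With 13 RN, alpha is 0.042-0.044 and power about 0.85.

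**Cut-off by attained total.** The largest c with alpha ≤ 0.05, keeping stage 1 as in Appendix A:

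| Lesions | Cut-off (RN) | Alpha | Power |
|---|---|---|---|
| 120 | 11 | 0.041 | 0.80 |
| 128 | 12 | 0.041 | 0.83 |
| 134 | 13 | 0.047 | 0.86 |
| 142 | 14 | 0.047 | 0.87 |
| 150 | 15 | 0.046 | 0.88 |

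**The case against.** The strongest reply is that the lesion total is the target. Section 4.4.3 speaks of completing all 134 lesions, section 6.4 calls 134 necessary, and 49 is only ever an estimate. On that reading the trial enrols until 134 is reached, the overshoot is a lesion or two, alpha stays below the stated 0.047 and power stays above the planned 0.80. I accept this as the more natural reading. The plan does not state it, however, and the alternative has a different error rate.

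A second reply is that, even with a hard stop at 49 patients, shortfalls and overshoots largely offset, so alpha averages only 0.049-0.064. That is also right, and only the widest assumed spread moves the average noticeably. But the total is known at the end. The error rate that bears on the claim is the one at that total, and a cut-off set in advance can control it.

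A reader might infer that the trial's type I error is really 0.112, or 0.164 with the count of 14. The documents do not support that. Those values hold only at 120 lesions, no section says that accrual stops short of 134, and the 0.164 includes a separate problem: 14 gives alpha 0.077 even at exactly 134, because a rejection number of 120 means 13 or fewer RN. Nor can one say that 134 will rarely be reached exactly. That is so with a stop at 49 patients (3-6%), but not with accrual to at least 134 (about 36%).

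**Conclusion.** The concern holds as a gap in the primary decision rule. The count in 4.4.3 has its stated meaning at one total only, and the plan settles neither what ends accrual nor what happens at another total. The size depends on the unstated stopping rule: small if accrual runs to at least 134 lesions, and material at individual totals if it ends at 49 patients, where close to half of trials would fall short.

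The values at each total and the cut-offs are exact given independent lesions, which section 6.4 assumes; correlation within patients would change them. The frequencies, averaged alphas and overshoot also rest on assumed spreads, since only the mean of 2.75 is given. This is worth correcting before results are known, but it does not show that the design is unsound.

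**What to change.** 1. In 6.4 and 4.4.3, state that whole patients are enrolled until at least 134 index lesions are in, and that 49 is the expected number of patients only. If a patient range is wanted, about 52-57 patients give 90% assurance of 134 lesions under the spreads assumed here; it should be labelled illustrative.
2. In 4.4.3 and Appendix A, replace the single count with the largest RN count whose exact two-stage alpha at 15% is at most 0.05 for the attained total: 13 at 134 and, for example, 11 at 120, 12 at 128, 14 at 142 and 15 at 150. The rows below 134 matter only if accrual closes short, and they keep a shortfall from inflating alpha. Recompute them if stage 1 is assessed on a number other than 52.
3. State beside the table that the cut-offs assume independent lesions.

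The cost is a short table and a sentence or two in each section, with no new data. The patient number becomes slightly less certain. Because counts are whole numbers, power dips just under 0.80 at some shortfalls (0.79 at 133 lesions with a cut-off of 12).

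### Section 4.4.3 lets a pass of the two-stage test be claimed as a 50% reduction in radiation necrosis, but the test can only reject a rate of 15% or more

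*Combined protocol and SAP*

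**What the plan says.** Section 4.4.3 gives the final decision rule. Once the trial has continued to 134 lesions, "if we find 14 or less lesions with radiation necrosis", the investigators would "claim that the study has met its objective of a 50% reduction in incidence of radiation necrosis (from 15% to 7.5"%). The sentence refers to Appendix A. Section 6.4 uses the same language for the sample size: "a total of 134 lesions are necessary to show a 50% effective reduction in radiation necrosis with our supplement".

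Appendix A counts freedom from RN as success. The design used is headed "Possible Designs For P0=0.850, P1=0.925, Alpha=0.050, Beta=0.200", with N1 = 52, R1 = 44, N = 134 and R = 120. Its Report Definitions state that "Alpha is the probability of rejecting that P<=P0 when this is true" and that "P1 is the response proportion of a good drug". R is the combined rejection number, so 120 or fewer RN-free lesions is a failure.

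The unit of analysis is the lesion. Section 6.4 follows the institution's earlier series: "Each lesion was treated independently when analyzing the incidence of radiation necrosis". Section 4.4.2 says results will be reported overall and by strata. Neither the protocol nor Appendix A plans a confidence interval or limits the conclusion drawn from a pass.

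**The concern.** In a Simon two-stage design the only hypothesis rejected is the null, here an RN-free proportion of 0.85 or less, which is an RN rate of 15% or more. The alternative of 0.925 (RN 7.5%) enters only through the power. Section 4.4.3 takes the alternative as the finding.

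All three designs in Appendix A share the same null. A pass of any of them rejects the same hypothesis, so the size of the reduction claimed comes from the choice of alternative and not from the data.

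This is the pre-specified conclusion of the primary analysis. Followed as written, it would report a halving of RN for results whose own estimate is well short of that, with no interval to show how little is excluded.

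**Working it through.** **Inputs.** Null RN 15% and alternative RN 7.5%; stage 1 of 52 lesions with R1 = 44; final N = 134 with R = 120 (all Appendix A). The cut-off of 14 RN is from section 4.4.3. Lesions are treated as independent, as in section 6.4.

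**On the RN scale.** Continuing needs at least 45 RN-free of 52, so at most 52 − 45 = 7 RN. Passing needs at least 121 RN-free of 134, so at most 134 − 121 = 13 RN. For true RN rate p and final cut-off c, the pass probability is

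F(c, p) = Σ over x = 0 to 7 of Bin(x; 52, p) × P[Bin(82, p) ≤ c − x].

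**Check against the plan's own figures.** At p = 0.15:

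- F(13) = 0.0471 (printed alpha 0.047).
- The probability of early termination is P[Bin(52, 0.15) ≥ 8] = 0.528 (printed 0.528).
- Average N = 52 + (1 − 0.5281) × 82 = 90.69 (printed 90.69).

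The printed beta of 0.200 does not reproduce. At RN 7.5%, F(13) = 0.856, so beta is 0.144; power is 0.800 at RN 8%. The argument here does not use beta.

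**Observed reduction at each count**, computed as 1 − (count/134)/0.15:

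| RN count | Observed rate | Reduction from 15% |
|---|---|---|
| 10 | 7.46% | 50% |
| 11 | 8.21% | 45% |
| 12 | 8.96% | 40% |
| 13 | 9.70% | 35% |
| 14 | 10.45% | 30% |

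Counts of 11 to 14 trigger the 50% claim in 4.4.3 although the estimate is below 50%.

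**Probability of making the claim:**

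| True RN | Cut-off 13 | Cut-off 14 |
|---|---|---|
| 15% (no reduction) | 0.047 | 0.077 |
| 12% | 0.24 | 0.33 |
| 10% (one-third reduction) | 0.51 | 0.61 |
| 7.5% (50% reduction) | 0.856 | 0.903 |

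These use the Appendix A first stage. Read literally, 4.4.3 continues if the eighth RN occurs at lesion 52 or later, which means at most 7 in the first 51. With cut-off 14 that gives 0.0776 at RN 15% and 0.612 at RN 10%, so little changes.

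**Intervals allowing for the two stages.** For an observed count k, the upper limit solves F(k, p) = 0.05 and the lower limit solves 1 − F(k − 1, p) = 0.05. Together they form a two-sided 90% interval that matches the one-sided 5% test.

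| RN count | 90% interval for RN | Reduction from 15% |
|---|---|---|
| 10 | 4.1% to 12.3% | 73% down to 18% |
| 13 | 5.8% to 14.9% | 62% down to 1% |
| 14 | 6.3% to 15.7% | upper limit above 15% |

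Ignoring the two stages, the one-sided 95% Clopper-Pearson upper limits are 14.98% at 13 and 15.9% at 14. Even 10 RN, an observed 50% reduction, is compatible with a true reduction of 18%. To reject RN of 7.5% or more at one-sided 5% would take 4 or fewer RN in 134: P[Bin(134, 0.075) ≤ 4] = 0.024, whereas 5 gives 0.058.

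**Sensitivity to within-patient correlation.** The documents give no value, so this is an assumed range. It takes 49 patients, 36 with three lesions and 13 with two (36 × 3 + 13 × 2 = 134), beta-binomial within patient, with 19 patients in stage 1.

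| Correlation | Upper limit at 13/134 | Type I error, cut-off 13 |
|---|---|---|
| 0.02 | 15.0% | 0.050 |
| 0.05 | 15.1% | 0.054 |
| 0.10 | 15.4% (rounded up from 15.35%) | 0.061 |
| 0.20 | 15.8% | 0.075 |

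**The case against.** The strongest reply is that this is a matter of wording. The sentence in 4.4.3 can be read as a go decision that names the pair of rates the design was built on, and it points to Appendix A, where the null, alternative and error rates are printed and defined. Section 6.4 is ordinary sample-size shorthand. Incidence is a primary endpoint, so a reader would see 13/134 or 14/134. The 0.51 to 0.61 is simply the pass probability of a Simon design between its null and alternative. It is true that the correction leaves the design alone and that the count would be reported. But 4.4.3 states what will be claimed, with the effect size and both rates, and 6.4 repeats it. The pass probability becomes the probability of an unsupported claim once a pass is equated with a 50% reduction.

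A second reply is that the 13 versus 14 mismatch and the within-patient correlation are separate matters. The interpretation point does stand without either, and the correlation range hardly affects the 0.51. The cut-off belongs here because the corrected conclusion fails at 5% if it is attached to 14. A result of 13 or fewer still excludes 15% whichever cut-off is printed; it is the rule with 14, and a result of exactly 14, that do not.

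Third, a reduction from 15% treats that rate as known, while section 2.2.1.1 cites 14% for the institution's own series. This stands: the bounds above leave out uncertainty in the reference rate, and a report should say so.

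**Conclusion.** The concern holds. A pass supports an RN rate below 15% and nothing stronger; 7.5% is the design alternative. Section 4.4.3 would claim a 50% reduction at 11 to 14 RN, where the observed reduction is 45% to 30%. It would do so with probability 0.51 (cut-off 13) or 0.61 (cut-off 14) if the true reduction were one third. With the printed 14, the type I error of 0.077 means that the rule does not establish even a rate below 15% at one-sided 5%.

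These figures assume independent lesions and a fixed reference of 15%. At 13/134 the upper limit only just excludes 15%, and a modest positive within-patient correlation would remove that margin. The main point, what a pass can be said to show, does not depend on the correlation. The section should be fixed before the result is interpreted.

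**What to change.** 1. In section 4.4.3, align the final cut-off with Appendix A and replace the claim, for example: *If 13 or fewer of the 134 lesions have radiation necrosis (Appendix A, R = 120), we would conclude, treating lesions as independent, that RN incidence is below the reference rate of 15%; 7.5% was the design alternative.* This wording should not be paired with a cut-off of 14.
2. Add an estimate: *The observed incidence and its relative reduction from 15% will be reported with a two-sided 90% interval obtained by inverting the two-stage rule, which matches the one-sided 5% test. The interval assumes independent lesions and would be wider with positive within-patient correlation.* It should also say that 15% is treated as fixed, and how the interval is formed if the trial stops at stage 1.
3. In section 6.4, describe the 134 lesions as the number needed to test RN of 15% or more against a design alternative of 7.5%.

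Similar wording in Appendix A for the 10% and 5% designs concerns options not adopted; editing it is optional.

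The cost is wording and one interval, plus a more modest claim. The null, the alternative, the Appendix A design and the 134 lesions are unchanged. Using 13 in place of 14 lowers exact power at RN 7.5% from 0.903 to 0.856, still above the planned 0.80.

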#### **Summary Statements**

The optimal two-stage design to test the null hypothesis that  $P \le 0.850$  versus the alternative

that P>=0.950 has an expected sample size of 33.71 and a probability of early termination of

0.602. If the drug is actually not effective, there is a 0.049 probability of concluding that it is (the target for this value was 0.050). If the drug is actually effective, there is a 0.200 probability of concluding that it is not (the target for this value was 0.200). After testing the drug on 13 lesions in the first stage, the trial will be terminated if 11 or fewer respond. If the trial goes on to the second stage, a total of 65 lesions will be studied. If the total number responding is less than or equal to 59, the drug is rejected.

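### The Simon design counts 134 lesions from about 49 patients as independent, so the stated alpha of 0.047 holds only if within-patient correlation is zero

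*Combined protocol and SAP*

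**What the plan says.** Section 6.4 sizes the trial by lesion. It reports that in the institution's published study "patients recruited to the study had an average of 2.75 metastatic lesions", and continues: "Each lesion was treated independently when analyzing the incidence of radiation necrosis. Using this same method, a total of 134 lesions are necessary". Dividing 134 by 2.75 gives the estimate of 49 patients.

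Appendix A gives the design, a Simon two-stage plan with an RN-free lesion as success: "Possible Designs For P0=0.850, P1=0.925, Alpha=0.050, Beta=0.200". The chosen row has 52 lesions with R1 = 44 in stage one and 134 lesions with R = 120 overall, with alpha 0.047. The report definitions state that "R is the combined drug rejection number after both stages". The worked summary for the neighbouring 15% to 5% design confirms the convention, because with R1 = 11 "the trial will be terminated if 11 or fewer respond". So R = 120 means that 120 or fewer RN-free lesions reject the supplement, and success needs at least 121 RN-free, that is, at most 13 with RN.

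Section 4.4.3 makes both decisions on raw lesion counts. No section gives an ICC, a design effect, a clustered analysis or a patient-level endpoint.

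**The concern.** A binomial decision rule keeps its stated error rates only if lesions are independent. Lesions in one patient share that patient's characteristics. Hypertension and diabetes, named as stratifiers in 4.4.2.3, belong to the patient. So does steroid need in the first RN criterion of 4.4.6.2, "patient with radiographic changes with a requirement of steroid therapy". Some positive correlation is therefore plausible even if the supplement does nothing. Shared adherence is not part of this argument: if the supplement has no effect, taking or missing it creates no correlation in RN.

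Positive correlation leaves the expected RN count unchanged but widens its spread, so under the null a low count is more likely than the binomial says. The trial is single-arm, and its success claim is one lesion count set against a historical 15%, so the error rate of that count is what protects the conclusion.

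**Working it through.** **Inputs.** From Appendix A: RN-free proportion 0.85 under the null and 0.925 under the alternative; n1 = 52, R1 = 44, N = 134, R = 120. From 6.4: mean 2.75 lesions per patient. The ICC and the distribution of lesions per patient are not in the documents and are assumed below.

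**Reproducing the plan (ICC 0).**

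- Early termination: P(X1 ≤ 44 | 52, 0.85) = 0.528, as printed.
- Average N: 52 + (1 − 0.5281) × 82 = 90.69, as printed.
- Alpha: sum over x1 = 45 to 52 of P(X1 = x1 | 52, 0.85) × P(X2 ≥ 121 − x1 | 82, 0.85) = 0.0471. Printed: 0.047.
- Power, by the same sum at 0.925, is 0.856. Beta is therefore 0.144, not the printed 0.200, so the rule has more power than stated.
- Patients: 134 / 2.75 = 48.7, rounded to 49.

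The stated alpha is thus the zero-correlation value.

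**Allowing for clustering.** Each patient's RN probability is drawn from a Beta distribution with mean 0.15 (null) or 0.075 (alternative) and the given ICC. Lesions are filled in patient order, with the interim look at lesion 52. The rule is the Appendix A one: at most 7 RN of 52, then at most 13 of 134. At least 200,000 null trials were simulated per cell. Three cluster-size patterns were used, each with mean 2.75 or close to it.

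| ICC | Alpha, 2 or 3 lesions per patient | Alpha, 1 + Poisson(1.75) | Alpha, geometric | Power at 7.5% RN |
|---|---|---|---|---|
| 0 | 0.047 | 0.047 | 0.047 | 0.86 |
| 0.02 | not run | 0.051 | not run | 0.85 |
| 0.05 | 0.054 | 0.056 | 0.059 | 0.84 |
| 0.1 | 0.061 | 0.065 | 0.073 | 0.82 to 0.83 |
| 0.2 | 0.075 | 0.082 | 0.096 | 0.79 to 0.82 |
| 0.3 | 0.089 | 0.098 | 0.117 | 0.77 to 0.80 |

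As a rough guide, with equal clusters the design effect is 1 + (2.75 − 1) × ICC. That is 1.0875 at ICC 0.05 and 1.175 at 0.1, so 134 lesions carry the information of about 134 / 1.0875 = 123 and 134 / 1.175 = 114.

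**What ICC is reasonable?** Suppose one binary patient factor is present in a fraction q of patients, with RN probabilities pA (absent) and pB (present) averaging 15%. Then ICC = q(1 − q)(pB − pA)² / (0.15 × 0.85). For q = 0.5 and odds ratio 3, pA = 0.084 and pB = 0.216, giving 0.25 × 0.132² / 0.1275 = 0.034. Over q from 0.3 to 0.5 (assumed), the ICC is about 0.015 at odds ratio 2, 0.034 to 0.039 at 3, and 0.051 to 0.063 at 4. A range of 0.02 to 0.10 is a fair working assumption; 0.2 and 0.3 serve only as upper bounds.

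**A separate mismatch.** Section 4.4.3 claims success "if we find 14 or less lesions with radiation necrosis", whereas Appendix A allows 13. With no clustering, the cut-off of 14 has exact alpha 0.077. Section 4.4.3 takes its first look when 8 RN lesions have occurred and adds: "If at that stage, we have 52 or more lesions in the study then that would confirm we should continue". This can be read as continuing with 8 RN in 52, where R1 = 44 stops. On that reading alpha is 0.081 at ICC 0, 0.090 to 0.097 at ICC 0.05 and 0.099 to 0.113 at ICC 0.1.

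**The case against.** The strongest reply is that the effect is small where the ICC is realistic. One patient factor with an odds ratio of 2 to 3 gives an ICC of about 0.015 to 0.04, and alpha is then roughly 0.050 to 0.055 against a target of 0.050 in a phase II study. Several features point to low correlation: the Follow Up Form scores RN by location, the steroid criterion is one of four and also requires radiographic change, and dose and lesion volume can differ within a patient. This stands, and it limits the size of the concern.

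Second, the per-lesion unit is declared openly and matches the study that supplies the benchmark. That keeps the point estimate comparable. It does not protect the stated alpha or the precision of the estimate.

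Third, the cut-off mismatch in 4.4.3 adds about 0.03 to alpha, more than clustering does at ICC 0.1 (about 0.014 to 0.026). That is correct. It is a different error, does not strengthen the clustering argument, and should be resolved first.

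Fourth, any reset cut-off depends on a cluster-size distribution that the documents do not give. This also stands, and is why the examples below are illustrations rather than prescriptions.

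**Conclusion.** The concern holds and should be fixed. The printed 0.047 is exact for the Appendix A rule at ICC 0, and positive correlation raises it. The target of 0.050 is reached at an ICC of about 0.02 (simulated alpha 0.051) and exceeded at 0.05 under all three cluster-size patterns. The excess over 0.047 is about 0.01 at ICC 0.05 and 0.014 to 0.026 at ICC 0.1. Power of the unchanged rule stays above 0.80 up to ICC 0.1 and near 0.80 beyond that, so the harm is an understated false-positive risk rather than lost power.

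The direction is firm for any positive ICC. The size rests on an assumed ICC, an assumed spread of lesions over patients and a beta-binomial model.

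**What to change.** All of this should be done before outcome data are seen, because a cut-off moved afterwards is not credible.

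1. Reconcile 4.4.3 with Appendix A: 14 or 13 RN at the end, and whether 8 RN in 52 continues or stops.
2. In 6.4, state that lesions are clustered within patients, and give an assumed ICC with a range and the expected spread of lesions per patient.
3. In 4.4.3, set the final cut-off under that ICC and restate alpha and power over the range.
4. Report RN incidence with a patient-clustered confidence interval beside the count rule, for example from a beta-binomial model or from GEE with a small-sample correction.

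Illustrations, with at most 7 RN of 52 at stage one and 1 + Poisson(1.75) lesions per patient:

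| Assumed ICC | Final rule | Alpha | Power |
|---|---|---|---|
| 0.05 | 12 or fewer of 129 | 0.046 | 0.81 |
| 0.1 | 12 or fewer of 131 | 0.048 | 0.78 |
| 0.1 | 12 or fewer of 134 | 0.040 | 0.76 |
| 0.3 | 11 or fewer of 134 | 0.044 | 0.66 |

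**Cost.** At ICC 0.05 the first rule gives alpha 0.044 to 0.049 and power 0.80 to 0.81 across the three patterns. It needs 129 / 2.75 = 46.9, about 47 patients against 49. The room comes from the design's actual power of 0.856. Both targets can be met up to an ICC of about 0.06 with Poisson sizes, but with geometric sizes they are narrowly missed there (0.052 and 0.798). At ICC 0.1, staying within 134 lesions puts stated power below 0.80, and the 131-lesion rule has alpha 0.055 with geometric sizes. Restoring all the information lost would take about 146 lesions (53 patients) at ICC 0.05 or 158 (58 patients) at 0.1.

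If the true ICC is 0, the stricter cut-off is conservative: 12 of 129 gives alpha 0.038 and power 0.82; 12 of 134 gives 0.027 and 0.79.
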